10.4 Intent-to-Treat (ITT) Population

The Intent-to-Treat (ITT) population consists of all randomized subjects who have at least one VR session.

The ITT population is the primary population to analyze efficacy endpoints. Demographic and baseline characteristics of the ITT population will also be presented. Subjects will be analyzed according to the treatment they received.

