10.2 Full Analysis Set (FAS)

The Full Analysis Set (FAS) consists of all subjects enrolled and randomized into the study.

The FAS population will be used for summaries of subject disposition, demographic and baseline characteristics. Subjects will be analyzed according to the treatment group they were assigned at randomization.

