11.18 Self-Evident Corrections

In some instances, spelling errors may be corrected in programs for 'Other, Specify' fields (free text). These will be reconciled and confirmed with sponsor before database lock.

12 Statistical Analyses

Planned or Actual treatment groups will use the following conventions:

- Enrolled Population - Planned treatment group
- FAS Population – Planned treatment group
- Safety Population – Actual treatment group
- ITT Population – Actual treatment group
- Per-protocol Population – Actual treatment group

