12.1 Subject Disposition

The number and percentage of subjects in screened, Enrolled Population, FAS population, Safety Population, Per-Protocol population and ITT population will be presented by treatment groups and total. Percentages for FAS population is based on Enrolled Population and percentages for all the other populations will be based on FAS population.

Number and percentage of subjects who completed the study, number and percentage of subjects who failed screening along with their reasons, number and percentage of subjects who terminated the study early along with their reasons will be summarized separately by treatment group and total. Reasons for screen failure will be displayed as in CRF. Percentages will be based on all screened subjects who signed ICF. Reason for discontinuation will be displayed in the descending order of "Total" column and percentages will be based on FAS population.

A flow diagram of subject disposition (CONSORT flow diagram) illustrating the progress of subjects throughout the study from screening to study completion/discontinuation will be provided.

Note that Enrolled Population and FAS population will be displayed by planned treatment and all other populations will be displayed by actual treatment.

Subject disposition information, status of inclusion exclusion criteria and subjects excluded from ITT analysis will be listed by subject who are screened.

Above analysis details are specified in DDP Table 14.1.1.1, Table 14.1.1.2, Figure 14.1.1.1, Listing 16.2.1.1, Listing 16.2.1.2 and Listing 16.2.3.1

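### The SAP's Intent-to-Treat set, primary for efficacy, is grouped by treatment received, so no efficacy comparison is as randomized; results change only if a kit is misallocated

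*SAP*

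**What the plan says.** SAP 10.4 defines the set: "The Intent-to-Treat (ITT) population consists of all randomized subjects who have at least one VR session". It gives the set its role: "The ITT population is the primary population to analyze efficacy endpoints". It then fixes the grouping: "Subjects will be analyzed according to the treatment they received".

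The grouping is not a stray sentence. The list of conventions that opens SAP Section 12 has "ITT Population – Actual treatment group", and the note in SAP 12.1 says "Enrolled Population and FAS population will be displayed by planned treatment and all other populations will be displayed by actual treatment".

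The FAS follows the opposite rule. SAP 10.2 states "Subjects will be analyzed according to the treatment group they were assigned at randomization", but limits its use: "The FAS population will be used for summaries of subject disposition, demographic and baseline characteristics".

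For the disposition table, SAP 12.1 bases the FAS percentage on the Enrolled Population and adds that "percentages for all the other populations will be based on FAS population". The same section bases the percentages for discontinuation reasons on the FAS.

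Protocol 15.2 defines the earlier modified ITT set without saying whether subjects are grouped by assigned or received treatment. SAP Section 13, item 7, replaces that set with ITT. Its stated reason is missing CEQ data, and it does not mention the grouping rule.

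**The concern.** Intent-to-treat means analysis by assigned arm. A set that carries the name but is grouped by device received invites readers of the report to assume a protection that is absent. By its definition in SAP 10.3 and 10.4, the ITT set has essentially the same members and the same grouping as the Safety set, and SAP Section 13 puts all 52 Safety subjects in it.

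Two things are at stake. First, Protocol 7.3.1 says the pilot is to inform a later registration trial, and the SAP plans between-arm tests on CEQ, LSAS and responder status. A subject regrouped by device received is no longer compared by randomization. Second, the tables can disagree about a subject's arm. A misallocated subject who drops out appears under the planned arm among the discontinuations and under the actual arm in retention.

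A mismatch is possible in principle. Protocol 9.3 has kits assigned by the IWRS and shipped from a depot straight to the subject, and Protocol 7.2.2 has the headsets look identical and keeps site staff out of the process.

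**Working it through.** **The plan's own figure.** SAP 4.2 gives 15 evaluable per arm and 25% attrition: 15 / (1 − 0.25) = 20 per arm, 40 in total. This reproduces. It is not in dispute and does not depend on the grouping rule.

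**Step 1: trace the arm rule for each output.**

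| Output | Set | Arm used | SAP section |
|---|---|---|---|
| Early terminations and reasons | FAS | planned | 12.1 |
| Size of Safety, ITT and PP sets | each set | count by actual, percentage on planned-arm FAS | 12.1 |
| CEQ | ITT, PP | actual | 12.8.1 |
| Retention, time-on-task | ITT | actual | 12.8.2 |
| LSAS, CGI-S, CGI-I, PGI-I, PHQ-9, responders | ITT | actual | 12.9 |

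No efficacy row uses the planned arm. One leftover: the responder-rate denominator in 11.17.8 still names the modified ITT set that Section 13 removed.

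**Step 2: assumptions for the size.** SAP Section 13 gives 52 subjects but no split by arm. Assume 26 randomized to each arm, all with a session, and one subject randomized to BES-100 who received BVR-100. Differences are BVR-100 minus BES-100.

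**Step 3: disposition table.** ITT as a percentage of FAS:
- BVR-100: 27/26 = 103.8%
- BES-100: 25/26 = 96.2%

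At the planned 20 per arm, the figures are 21/20 = 105.0% and 19/20 = 95.0%. A population above 100% of its own base is impossible.

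**Step 4: retention.** Assume 20/26 (76.9%) retained in each randomized arm, close to the 75% implied by the planned attrition. The as-randomized difference is 0.
- Moved subject was retained: 21/27 − 19/25 = 77.8% − 76.0% = +1.8 points.
- Moved subject dropped out: 20/27 − 20/25 = 74.1% − 80.0% = −5.9 points.

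At this retention rate the first case is the likelier one.

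**Step 5: mean difference (CEQ or LSAS).** Let the moved subject lie d SD from the mean of all others, set to 0. As randomized the difference is −d/26; as treated it is +d/27. The shift is d(1/26 + 1/27) = 0.0755d. The standard error is sqrt(2/26) = 0.277 SD.
- d = 0: no shift.
- d = 1: 0.08 SD, or 0.0755/0.277 = 0.27 standard errors.
- d = 2: 0.15 SD, or 0.151/0.277 = 0.54 standard errors.

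**Step 6: no misallocation.** Planned and actual arms coincide, and every shift above is zero.

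**The case against.** **The harm is hypothetical.** The documents report no wrong shipment. Protocol 9.2 to 9.4 provide kit numbers, a software identifier, accountability records for each subject and an unblinded team that confirms receipt. This stands. A reader might infer that the randomized comparison has already been lost or biased; the documents do not support that.

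**The protocol is silent on grouping, and SAP Section 2 lets the SAP prevail.** This stands in part. A reader might infer an undisclosed reversal of a protocol rule, but Protocol 15.2 has no such rule to reverse, and the SAP states its own openly in three places. Precedence still does not make an as-treated rule intent-to-treat.

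**FAS and ITT have different members, so their tables need not agree.** True for totals. It does not explain why one subject should sit in different arms, or why a percentage should mix two arm rules.

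**Grouping by device suits CEQ and time-on-task.** CEQ is completed after using the device, and SAP 11.17.3 has a separate time-on-task formula for each product. The point about formulas stands and the fix must address it. A CEQ summary by device used would be reasonable as a labelled supplement, but not as the only analysis under an ITT label.

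**This is a pilot.** Protocol 15.4.2 plans no formal hypothesis testing, and retention and time-on-task are descriptive. A reader might infer a threat to a confirmatory type I error. One sentence in Protocol 15.2 uses that language, but neither 15.4.2 nor SAP 8.2, which makes multiplicity adjustment not applicable, carries it through.

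**Conclusion.** The point holds on the text. The set labelled Intent-to-Treat is grouped by treatment received, is primary for all efficacy endpoints, and leaves no efficacy comparison as randomized. Section 12.1 also mixes actual-arm counts with planned-arm denominators.

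The consequence is conditional on a misallocated kit. The documents give no rate for such errors, so only the size per event can be stated. With one moved subject it is 1.8 to 5.9 points on retention, and 0.08 to 0.15 SD on a mean difference for a subject 1 to 2 SD out. These sizes rest on an assumed 26 per arm and, for retention, on 20 of 26 retained in each arm.

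This should be corrected because the label misdescribes the analysis and the correction is cheap, not because there is evidence of bias. A reader might also infer that regrouping would deliver a true ITT analysis. It would not: randomized subjects with no VR session remain excluded under 10.4.

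**What to change.** - **SAP 10.4 and the ITT line in Section 12:** group by the treatment assigned at randomization.
- **SAP 12.1:** conform the note on planned and actual display, and use the same arm for numerator and denominator. Counting every population by planned arm in the disposition table does this.
- **Safety:** keep actual treatment for safety outputs. SAP 12.10.5 places the C-SSRS summary on ITT while the appendix lists it under Safety; follow the appendix so that it stays by actual treatment.
- **Time-on-task:** derive each session with the 11.17.3 formula for the device actually used, then summarise by randomized arm.
- **Per-Protocol:** classify a misallocated kit as an important deviation that excludes the subject. Planned and actual arms then coincide in that set.
- **Description:** state in 10.4 that randomized subjects without a VR session are excluded, so the set is not read as full ITT. Record the grouping rule in Section 13.

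The cost is a few lines of SAP wording, one treatment variable in the efficacy programs and one derivation rule. The sample size is unchanged. If every kit matched its assignment, no efficacy result changes.

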10.5 Per-Protocol Population

The Per-Protocol population consists of all ITT subjects who have completed the 8-week intervention period without any important protocol deviations.

The PP population is the population used for supportive analysis of the primary endpoint. Demographic and baseline characteristics of the PP population will be presented. Subjects will be analyzed according to the treatment they received.

11 Analysis Variables

11.1 Population Flags

Population flags will be finalized and authorized by the Study Statistician and Sponsor prior to database lock as per definitions provided in Section 10. These flags will be included in the analysis datasets.

11.2 Treatment groups

All analyses will be summarized by treatment groups. The following treatment groups will be defined in the analysis datasets.

- BVR-100
- BES-100

11.3 Analysis Visits

All analysis datasets with measurements taken at more than one visit/time point will have analysis visit and timepoint as defined below.

Collected Visit	Analysis Visit
Screening	Visit 1 Screening
Randomization	Visit 2 Randomization
Week 1	Visit 3 Week 1
Week 2	Visit 4 Week 2
Week 4	Visit 5 Week 4
Week 6	Visit 6 Week 6
Week 8/ End of Study/ Early Termination	Visit 7 Week 8

A subject is considered to have attended any visit only if at least one assessment has been taken at the visit. As per section 11.10, derived baseline results will also be presented in summary tables.

11.3.1 Repeat Assessments

For safety and efficacy endpoints, if an unscheduled visit occurred on the same day as the scheduled visit, then it will be considered as a repeat for that assessment. Repeat and Unscheduled visits will not be considered for summary purpose but will be included in listing and baseline calculation.

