### **11.4.2. Columbia Suicide Severity Rating Scale**

The Columbia Suicide Severity Rating Scale (C-SSRS) will be administered by investigator site staff.

The C-SSRS is a tool designed to systematically assess and track suicidal adverse events (suicidal behavior and suicidal ideation) throughout the trial. The strength of this suicide classification system is in its ability to comprehensively identify suicidal events while limiting the over-identification of suicidal behavior. The scale takes approximately 5 minutes to administer ([Posner-2011](#)). The C-SSRS will be administered by a trained rater at the site. Subjects with Type 4 or Type 5 suicidal ideation at the Screening or Baseline visit will be excluded from entry into the study. Subjects with Type 4 or Type 5 suicidal ideation during the study will be discontinued from the study and referred to a mental health professional. At the Screening visit/Visit 1, the “Baseline/Screening” version of C-SSRS will be used. For all applicable visits onward, the “Since Last Visit” version of the C-SSRS will be used.

If a subject answers “yes” to “Suicidal Ideation” Item 4 (active suicidal ideation with some intent to act, without specific plan) or Item 5 (active suicidal ideation with specific plan and intent) on any post-Baseline C-SSRS assessment, the subject must be discontinued from the study, referred to the Investigator for follow-up evaluation, and followed until the event resolves; in addition, an associated AE must be reported.

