##### ***PART 2 (investigator site staff during telehealth Visit 4 (W2)/ Visit 5 (W4) / Visit 6 (W6)/ Visit 7 (W8/EOS)):***

During the last 3 days of Weeks 2, 4, 6, and 8, the investigator site staff will conduct telehealth study visits to complete the following assessments:

- Clinician administers C-SSRS. (Week 4 and Week 8 ONLY)
- Clinician administers LSAS.
- Clinician completes CGI-S.
- Clinician completes CGI-I.

- Collect AEs and concomitant medication changes.

All attempts will be made to ensure that each subject is assessed by the same study staff to minimize confounding bias due to changing assessors.

Unscheduled telehealth visits to complete/perform additional safety assessments, may be conducted as deemed necessary by the investigator site staff/subject.

After the completion of the telehealth portion of visit 7 with investigator site staff, the second part of the visit will be conducted separately by a member of the unblinded site support team where the Qualitative Interview will be completed as the final study assessment on the same day or within no later than 48 hours. During this visit, the unblinded site support team will instruct the patient to return the device and provide any necessary guidance/instructions.

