#### **11.5.5. Intervention Period (Weeks 3, 5, and 7)**

Independently at home by subject:

- Minimum of 3 required VR sessions.
- Subjects are encouraged to engage with optional content and to review content completed at any time.
- In the event that subjects require technical support or further VR program instructions, support will be provided by a designated unblinded site support team (ie, personnel external to the site and not involved in data collection).

There are no telehealth visits scheduled during these weeks; however, unscheduled telehealth visits to complete/perform additional safety assessments, may be conducted as deemed necessary by the investigator site staff/subject.

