#### **15.4.3.2 Suicidality Measure**

Frequency and severity of suicidal ideation and suicidal behavior as measured by the C-SSRS scale will be summarized by treatment for the overall post-Baseline period and by visit.

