7.3 Safety Endpoints

- Incidence of AEs.
- Incidence of SAEs.
- Incidence of UADEs.
- Frequency of subjects with suicidal ideation or suicidal behavior based on the C-SSRS.

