8.1 General Conventions

Level of significance for statistical tests will be 0.05 two-sided. All analyses will be done using SAS (version 9.4, SAS Institute Inc., Cary, NC, USA).

Safety endpoints will be analyzed in a descriptive manner. Continuous data will be reported using the following descriptive statistics:

- Number of observations (n)
- Mean and Standard deviation (SD)
- Median
- Minimum (min) and Maximum (max)
- 25th percentile and 75th percentile

Categorical data will be presented using frequency (n = number of subjects; m = number of events) and percentage (%).

Listings will be provided for all data recorded in eCRF to study subject profiles. All listings will be sorted by treatment, subject ID and date (if applicable). Unscheduled visit data will only be listed and not included in summaries.

All p-values will be displayed to four decimal places, with p-values less than 0.0001 presented as '<0.0001' and p-values greater than 0.9999 presented as '>0.9999'. Minimum and maximum values will be reported in the units of collection with 3 decimals being maximum value; the mean, median, 25th percentile and 75th percentile will be presented with 1 decimal place more and the standard deviation 2 decimal places more than the units of collection. Percentages for categorical summaries will be represented to 1 decimal place.

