12.10.5 Columbia- Suicide Severity Rating Scale (C-SSRS)

Number and percentage of subjects without suicidal ideation or suicidal behavior, with suicidal ideation, with suicidal behavior, and with suicidal behavior or ideation will be presented by treatment groups based on ITT Population. All C-SSRS data will be listed based on all Enrolled population.

Above analysis details are specified in DDP Table 14.3.3.1 and Listing 16.2.8.1.

13 Changes to Planned Analyses

- 1 Protocol (section 12.3) specifies 'Baseline demographic and clinical characteristics will be compared between groups with the use of the two-sample t-test and the Mann–Whitney test for continuous measurements with and without normal distribution, respectively'. But the statistical testing for baseline characteristics is being waived as per the recent discussion with the sponsor.
- 2 Protocol (section 12.9) mentions an analysis about differences in the mean change from CGI-S baseline score in the CGI-I and PGI-I at Weeks 2, 4, 6, and 8. This analysis is waived as per the recent discussion with sponsor.
- 3 An additional exploratory endpoint number [7](#) regarding the number of required BVR-100 and BES-100 sessions completed, is added in the section 7.4 as per the decision by sponsor clinical team.
- 4 Sentence "to ensure a reliable estimate of the standard deviations to power a future trial with 90% and an expected effect size between 0.3 and 0.7" in section 4.2 Sample Size Justification is removed because it is for future study not for this current study.
- 5 Per-protocol population definition in section 10.5 is updated to consider only ITT population as per the recent discussion with sponsor.
- 6 Baseline clinical characteristics is updated to follow the baseline definition in section 11.10 as per the recent discussion with sponsor.
- 7 In section 10.4, mITT (Modified Intent-to-Treat) population is removed from analysis and ITT population (efficacy population) has been added as per sponsor request. This population will be used for primary and secondary endpoint analysis.

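### The SAP keeps unscheduled and repeat C-SSRS results out of the safety summaries, so a subject whose only positive result is one of these can be tabulated as having no suicidal ideation or behavior

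*SAP*

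**What the plan says.** The safety endpoint in SAP 7.3 is a count of subjects: "Frequency of subjects with suicidal ideation or suicidal behavior based on the C-SSRS". Protocol 15.4.3.2 says that frequency and severity on this scale "will be summarized by treatment for the overall post-Baseline period and by visit". It does not exclude unscheduled results.

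The SAP restricts the data that can enter any summary. Section 8.1 states: "Unscheduled visit data will only be listed and not included in summaries". Section 11.3.1 treats a same-day unscheduled visit as a repeat and then states: "Repeat and Unscheduled visits will not be considered for summary purpose but will be included in listing and baseline calculation". SAP 11.16, which defines ideation and behavior by a yes answer at a visit, makes no exception. Nor does SAP 12.10.5, which tabulates "Number and percentage of subjects without suicidal ideation or suicidal behavior, with suicidal ideation, with suicidal behavior, and with suicidal behavior or ideation" by treatment group. Section 12.10.5 names neither an overall post-Baseline period nor a by-visit display.

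On timing, protocol 11.5.4 has the entry "Clinician administers C-SSRS. (Week 4 and Week 8 ONLY" in parentheses, and the schedule tables in both documents agree with it. Protocol 11.5.5 adds that "unscheduled telehealth visits to complete/perform additional safety assessments, may be conducted as deemed necessary by the investigator site staff/subject". On the form, protocol 11.4.2 says: "For all applicable visits onward, the “Since Last Visit” version of the C-SSRS will be used".

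**The concern.** Limiting by-visit tables to scheduled visits is a normal convention, because it keeps the rows comparable. It does not suit an endpoint that asks whether a subject ever had suicidal ideation or behavior during the intervention. For that question every post-Baseline assessment is relevant, and leaving some out can only lower the count.

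The table also has an explicit row for subjects without ideation or behavior. A subject whose positive result is set aside is therefore not left blank but reported as negative. At stake is the accuracy of the trial's only prespecified suicidality endpoint, in arms small enough that one subject changes what a reader sees.

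**Working it through.** The plan states no figure on this point, so there is nothing to reproduce. The check has two parts: following the rules through for one subject, and finding the weight of one case.

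**1. Which rule governs.** SAP section 2 says that the SAP overrides the protocol's statistical section where they differ. Protocol 15.4.3.2 therefore does not rescue the endpoint. SAP section 13, which lists changes to the planned analyses, mentions neither the exclusion of unscheduled C-SSRS data nor the absence of the overall post-Baseline summary.

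**2. One hypothetical subject.** Suppose the Week 4 C-SSRS is negative, an unscheduled C-SSRS in Week 5 is positive on ideation item 2, and Week 8 follows.

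| Meaning of last visit on the form | Week 8 result | SAP table | Overall post-Baseline count using all assessments |
|---|---|---|---|
| Includes the unscheduled contact | Can be negative | Without ideation or behavior | Positive |
| Last scheduled visit only | Positive, if the subject reports the event again | Positive | Positive |

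The documents do not say which meaning applies. Early-termination results are summarized with Week 8 (SAP 11.3 and 11.6), so the same reasoning covers an ET visit. A same-day repeat that turns positive is excluded under SAP 11.3.1 whichever meaning is used.

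**3. What other outputs would show.**

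- All C-SSRS data go into Listing 16.2.8.1 (SAP 12.10.5).
- Ideation items 4 and 5 on any post-Baseline C-SSRS require an AE report (protocol 11.4.2). The AE tables depend on onset relative to the first VR session, not on visit type (protocol 15.4.3, SAP 11.15), so the event reaches them. The AE and C-SSRS tables could then disagree about the same subject.
- For ideation items 1 to 3, and for behavior as such, protocol 11.4.2 sets no AE requirement. General AE collection under protocol 11.4.1 may or may not capture them.

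**4. Weight of a case.** Understatement in percentage points = 100 × k/n, where k is the number of subjects whose only positive result is unscheduled or a repeat, and n is the denominator. Inputs: n = 20 per arm planned (protocol 15.1); 52 subjects in the ITT population (SAP section 13), giving 52/2 = 26 per arm if evenly split, which is an assumption. The values of k are illustrative.

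| k | n = 20 | n = 26 | n = 52 (both arms) |
|---|---|---|---|
| 1 | 5.0 | 3.8 | 1.9 |
| 2 | 10.0 | 7.7 | 3.8 |
| 3 | 15.0 | 11.5 | 5.8 |

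With k = 1 in one arm and no other positive subject, the table would read 0 against 0 instead of 1 against 0.

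**The case against.** The strongest reply is that the rule may do little harm. The protocol does not name the C-SSRS as a procedure for unscheduled visits. The summary is descriptive, in a pilot, and no stopping rule depends on it. With about 52 subjects a positive record can be found by reading the listing. The PHQ-9, whose ninth item serves as a suicidality screen at entry, is completed at Weeks 2, 4, 6 and 8 and reviewed for potential AEs. An actual attempt would ordinarily meet the AE definition. Section 12.10.5 gives no visit structure, so its counts could be read as the overall summary, and the layout sits in a Data Display Plan that is not among these documents.

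Most of this stands and limits the consequence. It does not remove the fault. The C-SSRS is listed among the safety assessments, and protocol 11.4.2 speaks of any post-Baseline C-SSRS. Even if 12.10.5 is read as an overall summary, sections 8.1 and 11.3.1 still keep unscheduled and repeat results out of it.

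A reader might go further in four ways that the documents do not support:

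- **That a later scheduled C-SSRS must miss the event.** This depends on how last visit is understood, which is not stated.
- **That these events would appear in no safety output.** The listing and AE reporting cover part of the gap.
- **That the excluded cases are the most clinically real, or that most concerns arise between scheduled visits.** Neither document says so. The visit count is itself unsettled: the protocol synopsis and section 7.1 list the C-SSRS among the measures collected at Weeks 2, 4, 6 and 8, while 11.5.4 limits it to Weeks 4 and 8. These sections must be reconciled.
- **That the rule causes positive Screening answers to be counted under a treatment arm.** SAP 12.10.5 does not state a post-Baseline limit, but that is a separate silence and not a result of the unscheduled-visit rule.

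**Conclusion.** The concern holds in a limited form. As written, the SAP can place a subject with a positive unscheduled or repeat C-SSRS in the row for subjects without suicidal ideation or behavior, and the error runs only toward fewer cases. It requires that such an assessment takes place, that it is positive, and that the scheduled and ET assessments are negative.

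The main residual gap is ideation items 1 to 3, or behavior, not reported as an AE. Each case costs an arm 5.0 points at the planned size, or about 3.8 points with 26 per arm, taking all subjects in the arm as the denominator. The documents give no basis for estimating how many cases there would be, so these figures are the weight of one subject and not an expected bias. This should be fixed before the tables are run, but it does not threaten the study's primary conclusions.

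**What to change.** - In SAP 8.1 and 11.3.1, exempt the C-SSRS from the exclusion of unscheduled and repeat assessments.
- In SAP 12.10.5, count a subject as positive if any C-SSRS after the first VR session is positive, whether scheduled, unscheduled, repeat or ET. Present this for the overall post-Baseline period, as protocol 15.4.3.2 plans.
- Keep the by-visit rows on scheduled visits, and show Screening and Baseline results separately.
- Record the clarification in SAP section 13.

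This needs no new data, since the SAP already lists all C-SSRS records. The cost is a few sentences and a changed record selection in one table program. The reported rates may be slightly higher.
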